6.9.3. Independent Data Monitoring Committee

A single review committee (IDMC) will be established to monitor the study while it is ongoing, including periodic reviews of safety data, and pre-specified analyses of efficacy data, as described below.

- The IDMC will include 2 Clinicians (external to Teva) with expertise in IBD and 1 external Statistician. The names of the external IDMC members will be included in the IDMC charter.
- The role of the IDMC will be to periodically monitor unblinded safety data to ensure the safety of study patients as well as efficacy data for pre-specified interim analysis, and make recommendations on study conduct.

- There will be an independent (external to the sponsor and the study team) statistical reporting team that will perform the planned unblinded analyses of interim efficacy and safety data for the IDMC to review.

The IDMC charter will provide details regarding procedures to protect the scientific integrity of the trial, conduct of the interim analysis, dissemination of results, and decision criteria in addition to pre-specified study stopping rules for safety.

Additional details on the procedures and conduct of the IDMC sessions will be described in the IDMC charter.

6.10. Total Blood Volume

The estimated maximum blood volume to be collected in this study is approximately 280 mL for each patient during the entire study. Details on blood volumes to be collected during the study are provided in the ICF and the Laboratory Manual.

7. ASSESSMENT OF EFFICACY

7.1. Assessments of Efficacy

The following efficacy assessments will be performed at the time points specified in [Table 1](#). Endoscopy and histology assessments will be scored centrally.

7.1.1. Modified Mayo Score (Ulcerative Colitis)

The modified Mayo score evaluates UC stage based on the following 3 parameters:

- stool frequency
- rectal bleeding
- endoscopic evaluation

Each parameter of the score ranges from 0 (normal or inactive disease) to 3 (severe activity) and the total score from 0 to 9, respectively ([Ulcerative Colitis: Clinical Trial Endpoints Guidance for Industry 2016, Naegeli et al 2018](#)).

7.1.2. Endoscopy

Endoscopy will be performed at screening and week 14 or the early termination visit. Assessments and procedures performed during the endoscopy, including biopsy collection, SES-CD, and modified multiplier (MM)-SES-CD, are described below.

7.1.2.1. Biopsy Collection

For patients with CD, an ileo-colonoscopy will be performed at screening and week 14. During each endoscopy, a total of 11 to 18 mucosal biopsies will be obtained from the area with the greatest inflammation in each segment at screening and at the same location at week 14 or early termination. If ulceration is present, biopsies should be taken from the edge of the largest ulcer. If no ulceration is present, then biopsies should be taken from the most affected area of the segment. If the mucosa appears normal (eg, at follow-up), then random biopsies of the segment should be obtained.

For patients with UC, a flexible sigmoidoscopy will be performed at screening and week 14 (colonoscopy may be performed instead for baseline endoscopy if not done in the prior 12 months). During each endoscopy, a total of 7 to 12 biopsies will be obtained from the area with the worst disease 15 to 25 cm from the anal verge. If ulceration is present, biopsies should be taken from the edge of the largest ulcer. If no ulceration is present, then biopsy should be taken from the most affected area. If mucosa appears normal (eg, at follow-up), then random biopsies should be taken from the area 15 to 25 cm from the anal verge.

Endoscopic biopsies will be evaluated by microscopic and histologic analyses, as well as for exploratory measures involving established and novel biomarkers of intestinal inflammation and fibrosis. There are several different approaches for obtaining these endoscopic biopsy samples, and the preferred procedures are described in the Laboratory Manual and Quick Reference Card.

Histology samples will be scored by qualified independent, blinded central readers and digitized to enable the use of digital pathology for histology endpoints adjudication and computational quantification of inflammation and fibrosis severity. Details of adjudication strategies will be provided in the associated charter.

7.1.2.2.Simple Endoscopic Score for Crohn's Disease

The SES-CD takes into account 4 parameters (presence of ulcers, percentage of ulcerated surfaces, affected surface, and presence of strictures) that need to be scored in 5 bowel segments (the rectum, sigmoid and left colon, transverse colon, right colon, and ileum) ([Daperno et al 2004](#)).

7.1.2.3.Modified Multiplier-Simple Endoscopic Score for Crohn's Disease

The MM-SES-CD is an endoscopic scoring tool, which takes into consideration each individual parameter's prognostic value for achieving endoscopic remission while on active therapy ([Narula et al 2021](#)).

7.1.2.4.Robarts Histopathology Index (Ulcerative Colitis)

The Robarts Histopathology Index (RHI) final score is obtained by combining the subscores of 4 main items:

- chronic inflammatory infiltrate level (4 levels)
- lamina propria neutrophils (4 levels)
- neutrophils in the epithelium (4 levels)
- erosion or ulceration (4 levels)

The 4 components are classified from 0 to 3, yielding a final score that ranges between 0 and 33 ([Mosli et al 2017](#)).

7.1.2.5.Geboes Score (Ulcerative Colitis)

Geboes score is a scoring system for microscopic disease activity that incorporates a number of histological items classified in 5 grades ([Mosli et al 2014](#)).

7.1.2.6.Global Histologic Activity Score (Crohn's Disease)

The Global Histologic Activity Score consists of 8 items assessing acute and chronic inflammatory changes, epithelial damage, and the extent of inflammation (ie, the proportion of biopsy specimens affected). Each of the 8 items is scored, with the totals subsequently added together ([D'Haens et al 1998](#)).

7.1.3. Crohn's Disease Activity Index

The CDAI ([Yoshida 1999](#)) consists of 8 factors added up after adjustment with a weighting factor:

- Number of liquid or soft stools each day for 7 days \times 2
- Abdominal pain (graded from 0 to 3 on severity) each day for 7 days \times 5

- General well-being, subjectively assessed from 0 (well) to 4 (terrible) each day for 7 days \times 7
- Presence of complications \times 20
- Taking Lomotil, Imodium, or opiates for diarrhea \times 30
- Presence of an abdominal mass (0 as none, 2 as questionable, 5 as definite) \times 10
- Hematocrit of <0.47 in men and <0.42 in women \times 6
- Percentage deviation from standard weight \times 1

7.1.4. Two-item Patient-Reported Outcome (Ulcerative Colitis and Crohn's Disease)

UC: The 2-item patient-reported outcome (PRO2) includes daily evaluation of the 2 subjected items of the Mayo score: stool frequency and rectal bleeding. Each parameter of the score ranges from 0 (normal or inactive disease) to 3 (severe activity) and the total score from 0 to 6, respectively ([Dragasevic et al 2020](#), [Jairath et al 2015](#)).

CD: PRO2 is the sum of the daily stool frequency (0 to 3) and abdominal pain (0 to 3) from the CDAI ([Khanna et al 2015](#)).

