1.3. Schedule of Activities

Study procedures and assessments with their time points are presented in [Table 1](#). Detailed descriptions of each method of procedures and assessments are provided in Section [7](#) (efficacy assessments), Section [8](#) (safety assessments), and Section [9](#) (pharmacokinetic and other assessments). Study procedures and assessments by visit are listed in [Appendix A](#).

Exclusionary laboratory values can be retested once during the screening period. If the retested laboratory value(s) remain(s) exclusionary, the subject will be considered a screen failure. Redrawing samples if previous samples were unable to be analyzed would not count as a retest since previous result was never obtained.

Table 1: Study Procedures and Assessments

Study period	Screening (-42 to -1)	Induction period								Follow-up ^{a,b}	Early termination ^b	
		Treatment period ^a										
Study visit	Screening	1	2	3	4	5	6	7	8	9		
Study week	Week -6 to -1	Week 0	Week 2	Week 4	Week 6	Week 8	Week 10	Week 12	Week 14	Week 18		
Study day	Day -42 to -1	Day 1	Day 15	Day 29	Day 43	Day 57	Day 71	Day 85	Day 99	Day 127		
Visit window	N/A	N/A	±3 days based on previous visit									
Enrollment procedures												
Informed consent ^c	X											
Inclusion/exclusion criteria	X	X										
Demographics and medical history	X											
Vital signs												
Vital signs measurements ^d	X	X	X	X	X	X	X	X	X	X	X	
Weight (lb or kg)	X	X		X		X		X	X	X	X	
Height (in or cm)	X											
Medical procedures												
Full physical exam	X								X	X	X	
Brief physical exam				X		X		X				
ECG (12-lead) ^e	X			X		X			X		X	
Endoscopy												
Endoscopy ^f	X ^g								X		X	
Disease activity analysis												
Modified Mayo score (UC only)	X								X		X	

Study period	Screening (-42 to -1)	Induction period								Follow-up ^{a,b}	Early termination ^b
		Treatment period ^a									
Study visit	Screening	1	2	3	4	5	6	7	8	9	
Study week	Week -6 to -1	Week 0	Week 2	Week 4	Week 6	Week 8	Week 10	Week 12	Week 14	Week 18	
Study day	Day -42 to -1	Day 1	Day 15	Day 29	Day 43	Day 57	Day 71	Day 85	Day 99	Day 127	
Visit window	N/A	N/A	±3 days based on previous visit								
Stool frequency and Rectal bleeding Mayo sub-scores (PRO2 UC) ^h	X		X	X	X	X	X	X	X		X
Robarts Histopathology Index (UC only)	X								X		X
CDAI score (CD only)	X			X		X		X	X		X
Stool frequency and Abdominal pain (PRO2 CD) ^h	X		X	X	X	X	X	X			X
SES-CD (CD only)	X								X		X
MM-SES-CD (CD only)	X								X		X

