
A secondary objective of the study is to evaluate the efficacy of 2 different doses of TEV-48574 sc administered Q2W in adult patients with IBD (moderate to severe UC or CD) as assessed by multiple standard measures at week 14.
	
The secondary efficacy endpoints to be measured in patients with moderate to severe UC are as follows:
 
 • Clinical response at week 14, defined as a decrease from baseline in the modified (9-point rectal bleeding, stool frequency, and endoscopy) Mayo score of at least 2 points AND at least a 30% reduction from baseline with either a decrease in rectal bleeding subscore of at least 1 or an absolute rectal bleeding subscore of less than or equal to 1 • Endoscopic improvement defined as a Mayo endoscopic subscore of 0 or 1 at week 14 • Endoscopic remission defined as a Mayo endoscopic subscore of 0 at week 14 • Clinical response defined as decrease from baseline of at least 50% in 2-item patient-reported outcome (PRO2; rectal bleeding and stool frequency) at week 14 • Clinical remission defined as score of rectal bleeding = 0 and stool frequency = 0 on the PRO2 scale at week 14 
The secondary efficacy endpoints to be measured in patients with moderate to severe CD are as follows:
 
 • Clinical response defined as a ≥ 100-point decrease in Crohn’s Disease Activity Index (CDAI) score from baseline at weeks 4, 8, 12 and 14 • Clinical remission defined as a CDAI score < 150 at week 14 • Clinical response defined as a decrease from baseline of at least 50% in PRO2 (PRO2 is defined as having 2 components, abdominal pain and stool frequency) at week 14

Objectives	Endpoints
	
 • Clinical remission defined as abdominal pain ≤ 1 and stool frequency ≤ 3 on the PRO2 scale at week 14 • Endoscopic response defined as a decrease in modified multiplier (MM)-SES-CD of $>50\%$ from baseline at week 14

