3.3. Exploratory Objectives and Endpoints

The exploratory objectives and endpoints are:

Objectives	Endpoints

An exploratory objective of the study is to evaluate the efficacy of 2 different doses of TEV-48574 sc administered Q2W in adult patients with IBD (moderate to severe UC or CD) as assessed by multiple standard measures.
	
The exploratory efficacy endpoints to be measured in patients with moderate to severe UC are as follows:
 
 • Clinical response defined as decrease from baseline of at least 50% in 2-item patient-reported outcome (PRO2; rectal bleeding and stool frequency) at weeks 2, 4, 6, 8, 10, and 12 • Clinical remission defined as score of rectal bleeding = 0 and stool frequency = 0 on the PRO2 scale at weeks 2, 4, 6, 8, 10, and 12 • Histological remission defined as a Robarts Histopathology Index of ≤ 5 at week 14 • Histological remission defined as Geboes index score ≤ 3.1 at week 14 
The exploratory efficacy endpoints to be measured in patients with moderate to severe CD are as follows:
 
 • Clinical response defined as a decrease from baseline of at least 50% in PRO2 (PRO2 is defined as having 2 components, abdominal pain and stool frequency) at weeks 2, 4, 6, 8, 10, and 12 • Clinical remission defined as abdominal pain ≤ 1 and stool frequency ≤ 3 on the PRO2 scale at weeks 2, 4, 6, 8, 10, and 12 • Endoscopic remission defined as SES CD score of 0-2, or SES CD score of 0-4, with no individual sub score > 1 at week 14 • Histologic response defined as a $\geq 50\%$ decrease in Global Histologic Activity Score from baseline at week 14

An exploratory objective of the study is to evaluate the safety and tolerability of 2 different doses of TEV-48574 sc administered Q2W in adult patients with IBD (moderate to severe UC or CD).
	
 • Use of concomitant medication • Device-related adverse events and malfunctions (for the commercial sc infusion system)

Objectives	Endpoints

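### The Crohn's PRO2 stool item is scored 0 to 3 in Section 7.1.4 but is a stool count in the CDAI it is taken from; on the 0 to 3 scale the remission cut-off of 3 excludes nobody

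*Protocol*

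**What the plan says.** The definition of the instrument is in protocol Section 7.1.4: "CD: PRO2 is the sum of the daily stool frequency (0 to 3) and abdominal pain (0 to 3) from the CDAI". For ulcerative colitis the same section says: "Each parameter of the score ranges from 0 (normal or inactive disease) to 3 (severe activity) and the total score from 0 to 6".

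The stated source of the Crohn's items is the CDAI. Section 7.1.3 describes its stool item as "Number of liquid or soft stools each day for 7 days" and its pain item as "Abdominal pain (graded from 0 to 3 on severity) each day for 7 days". The first is a count with no stated upper limit; only the second is a 0 to 3 grade.

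Two Crohn's endpoints use the instrument:

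- **Remission.** Section 3.1, repeated in the synopsis, has as a secondary endpoint: "Clinical remission defined as abdominal pain ≤ 1 and stool frequency ≤ 3 on the PRO2 scale at week 14". Section 3.3 applies the same thresholds as an exploratory endpoint at weeks 2, 4, 6, 8, 10 and 12.
- **Response.** Section 3.1 has: "Clinical response defined as a decrease from baseline of at least 50% in PRO2 (PRO2 is defined as having 2 components", measured at week 14. Section 3.3 repeats it at the six earlier visits.

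Table 1, footnote h, says that patients enter stool frequency and abdominal pain daily in a handheld e-diary. It does not say whether stool frequency is entered as a count or as a grade.

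**The concern.** Three statements do not fit together: a 0 to 3 stool score, a source instrument in which that item is a count, and a remission cut-off of 3. Under the first, the cut-off sits at the top of the scale and the stool half of a two-item definition does nothing. Under the second, the cut-off does real work and the bracketed range in Section 7.1.4 is the wrong part. The protocol gives no rule for turning a count into a 0 to 3 score.

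At stake is whether a named secondary endpoint measures what its name says. On the 0 to 3 reading, a patient at the worst stool score with pain of 1 counts as in clinical remission. The percentage change behind the 50% response endpoint also depends on the scale. If the choice between count and grade were left until treatment codes are known, it would be a choice of endpoint made with the data in view.

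**Working it through.** The protocol states no figure to reproduce here, so the check is an enumeration of possible scores.

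**Inputs.** Stool score 0, 1, 2 or 3 and pain score 0, 1, 2 or 3 (Section 7.1.4). Remission rule: pain ≤ 1 and stool ≤ 3 (synopsis, Sections 3.1 and 3.3).

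**Step 1: the 0 to 3 scale as written.**

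| Condition | Combinations meeting it |
|---|---|
| All combinations, 4 × 4 | 16 |
| Stool ≤ 3 | 16 |
| Pain ≤ 1 | 8 |
| Both | 8 |

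The 8 that meet both are the same 8 that meet pain ≤ 1. Averaging over 7 days does not help, because a mean of scores between 0 and 3 cannot exceed 3. Stool 3 with pain 1, a total of 4 out of a possible 6, satisfies the rule.

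**Step 2: stool frequency as a count.** The range 0 to 10 is an assumption for illustration only. There are 11 × 4 = 44 combinations. Pain ≤ 1 is met by 11 × 2 = 22; both conditions are met by 4 × 2 = 8. The stool condition now removes 14 of the 22. These are numbers of score combinations, not proportions of patients.

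**Step 3: the response endpoint.** Take a patient whose pain falls from 3 to 0 and whose stools do not change, at the top of each range.

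- Graded stool item, simple sum: 3 + 3 = 6 falls to 3 + 0 = 3, a decrease of 3/6 = 50%. Responder.
- Count of 10 (same illustrative range), simple sum: 10 + 3 = 13 falls to 10, a decrease of 3/13 = 23%. Not a responder.
- Count of 10 with the CDAI weights of Section 7.1.3 (2 for stools, 5 for pain): 20 + 15 = 35 falls to 20, a decrease of 15/35 = 43%. Not a responder.

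The same course of symptoms is classified differently depending on the scale. Naming the CDAI as source also leaves open whether its weights carry over.

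**Step 4: where it applies.** Remission is assessed at 7 Crohn's time points: week 14 as a secondary endpoint and six exploratory visits. CDAI is scheduled after baseline at weeks 4, 8, 12 and 14 only, so at weeks 2, 6 and 10 PRO2 depends on the diary without a CDAI at the same visit.

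**The case against.** The strongest reply is that this is one wrong bracket. Section 7.1.4 itself says that the items come from the CDAI, where stool frequency is a count. If sites and programmers use the count, the cut-off of 3 discriminates and no patient is misclassified. That is a fair reading and probably the intended one. But the protocol also states a range, and no other section overrides it. Someone building the diary or the derivation from Section 7.1.4 would follow what it says. This is a stated rule that conflicts with others, not detail left to the SAP.

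Four stronger inferences are not supported:

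- **That every Crohn's patient will pass the stool criterion.** This is true only if the 0 to 3 scale is actually used, which the protocol does not settle.
- **That an inflated placebo rate will hide any drug effect on stools.** Dropping a condition cannot lower a remission rate, but that applies in every arm and no rates are available to size it. Stool frequency still enters the CDAI endpoints and the PRO2 response endpoint.
- **That the trial's main conclusions are at risk.** The Crohn's primary endpoint is SES-CD response. Section 10.1, the success rule in Section 10.5.4.1 and Appendix L do not use PRO2. Secondary comparisons carry nominal p-values (Section 10.5.4.4).
- **That week 14 data will be missed.** In Table 1 the Crohn's PRO2 row is blank at week 14, but Appendix A lists the assessment at visit 8 and the diary is daily. This is an editorial mismatch.

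**Conclusion.** The conflict is real and lies in the protocol's own wording. Conditional on the 0 to 3 stool scale being applied as written, the stool criterion is always met and Crohn's PRO2 remission reduces to abdominal pain of at most 1 at all 7 time points. If a count is used instead, the criterion works and only the range in Section 7.1.4 is wrong. Under either reading, the PRO2 response endpoint is not fully defined until the scale and the way of combining the two items are fixed.

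Of the five Crohn's secondary efficacy endpoints, one (PRO2 remission) is directly affected and a second (PRO2 response) depends on the scale; the remaining uses are exploratory. The primary endpoint, sample size and operating characteristics do not change. It should be corrected before unblinding, but it does not threaten the trial's primary analysis. That the 0 to 3 range was carried over from the ulcerative colitis item is plausible but cannot be shown from the protocol.

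**What to change.** 1. In Section 7.1.4, replace the 0 to 3 range for Crohn's stool frequency with the daily number of liquid or soft stools, as in Section 7.1.3. Keep 0 to 3 for abdominal pain.
2. Apply the remission cut-off of 3 to that count, averaged over the same diary window as abdominal pain, and use this definition for the synopsis, Section 3.1 and Section 3.3 endpoints.
3. State how the count and the pain score are combined for the 50% response: simple sum or CDAI weights.
4. Confirm that the e-diary of footnote h records a count, and that it does so for weeks 2, 6 and 10, where no CDAI is scheduled.
5. As an editorial correction, align the blank week 14 cell for Crohn's PRO2 in Table 1 with Appendix A, visit 8.

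If the diary already records counts, the cost is one corrected definition and one table cell, with no new data. If it records only grades at some visits, counts may not be recoverable there, and the affected exploratory time points would need to be redefined or dropped. Either way, the decision should be documented before treatment codes are released.

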8. ASSESSMENT OF SAFETY

In this study, safety will be assessed by qualified study personnel by evaluating reported adverse events, clinical laboratory test results, vital signs measurements, ECG findings, use of concomitant medication, local tolerability, and device-related adverse events and malfunctions.

Device deficiencies that are not associated with an adverse event, as well as those that have the potential to cause a serious adverse event, are covered in [Appendix G](#).

There will be an IDMC to monitor safety in this study (Section [6.9.3](#)).

8.1. Adverse Events and Adverse Device Effects

8.1.1. Definition of an Adverse Event

An adverse event is any untoward medical occurrence in a patient or clinical investigation patient administered a pharmaceutical product and which does not necessarily have to have a causal relationship with this treatment.

An adverse event can, therefore, be any unfavorable and unintended physical sign, symptom, or laboratory parameter that develops or worsens in severity during the course of this study, or significant worsening of the disease under study, or of any concurrent disease, whether or not considered related to TEV-48574.

Accordingly, an adverse event can include any of the following:

- a new condition or the worsening of a pre-existing condition
- intercurrent illnesses
- physical injuries and the mechanism that caused the injury
- events possibly related to concomitant medication
- drug or drug/device or device/device interactions
- events occurring during diagnostic procedures or during any washout phase of this study
- laboratory or diagnostic test abnormalities

(Note: Abnormal laboratory or diagnostic test results at the screening visit that preclude a patient from entering the study or receiving study treatment are not considered adverse events.)

IBD manifestations are efficacy variables for this study and should be captured on the relevant specific CRF; accordingly, these events should not be recorded as adverse events unless assessed as more severe than the patient's usual disease course. Extraintestinal manifestations of the patient's disease (eg, arthralgias, arthritis, or uveitis) that develop or worsen during the study should be reported as adverse events. IBD manifestations that are more severe than the patient's usual course of disease and meet the criteria for a serious adverse event (eg, required hospitalization) should be reported as a serious adverse event.

